6.3. Exploratory Analyses

6.3.1. Immunogenicity Endpoints of Exploratory Analyses

The immunologic endpoints for exploratory analyses are as follows:

- GMT of anti-JE neutralizing antibody at Year 4 prior to a booster dose of CD-JEV, 7 days, and 28 days after the booster dose as measured by PRNT-50.
- GMT ratio between 7 days after the booster dose and Year 4 prior to the booster dose and between 28 days after the booster dose and Year 4.

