- The difference in seroconversion rates between Groups A and B will be calculated along with the 95% CI of the difference using the Newcombe-Wilson method without continuity correction.
- The GMTs at 7 days and 28 days post the booster dose will be further compared to the GMTs at Year 4 prior to the booster dose using a paired t-test to evaluate the magnitude of increase in GMTs by study group. The GMT ratio between 7 days post the booster dose and Year 4 and between 28 days post the booster dose and Year 4 will be provided along with its 95% CI.
- Reverse cumulative distribution curves will be plotted for participants as anti-JE neutralizing antibody titer (x-axis) versus the proportion of participants with a titer of at least certain level (y-axis) at 7 and 28 days post the booster dose.

In addition, the booster response analyses on selected immunogenicity endpoints will be repeated on subgroups defined by seroprotection status of participants at Year 4 post primary CD-JEV vaccination.

Listing of serology results corresponding to each blood collection at participant-level will be provided.

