6.3.2. Exploratory Immunogenicity Analysis

The antibody response to a booster dose of CD-JEV will be examined on the following two subgroups:

- Primed group includes participants who will be seronegative for anti-JE immunoglobulin M (IgM) prior to the booster dose (Year 4) and 7 days after the booster dose and who will have a 4-fold or higher response in anti-JE neutralizing antibody titer at 7 days post the booster dose in relation to pre-booster anti-JE neutralizing antibody titer at Year 4.
- Unprimed group consists of participants who will be seronegative for anti-JE IgM at Year 4 prior to the booster dose, who will not have a 4-fold or higher response in anti-JE neutralizing antibody titer at 7 days post the booster dose in relation to pre-booster anti-JE neutralizing antibody titer at Year 4, and who will seroconvert from negative (anti-JE neutralizing antibody titer $< 1:10$) to positive (anti-JE neutralizing antibody titer $\geq 1:10$) between Year 4 prior to the booster dose to 28 days after the booster dose.

GMTs of anti-JE neutralizing antibody along with their 95% CI will be provided for primed group and unprimed group at Year 4 prior to the booster dose, 7 days, and 28 days after the booster dose.

The GMTs at 7 days and 28 days post booster dose will be further compared to the GMTs at Year 4 prior to the booster dose using a paired t-test to evaluate the magnitude of increase in GMTs for primed group and unprimed group. The GMT ratio between 7 days post the booster dose and Year 4 and between 28 days post the booster dose and Year 4 will be provided along with its 95% CI.

7. Safety Analyses

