- The number and proportion of participants with at least one SAE occurring within 28 days of the booster dose along with 95% CI of the proportion will be presented by study group. The SAEs will be summarized by maximum severity and relationship to the booster vaccination for each study group. The total number, maximum severity, relationship to the booster vaccination, onset date, status/outcome, duration for resolved cases (resolution date – onset date + 1), and medication given of SAEs will be also summarized by study group. Summaries will be repeated for SAEs found to be related the booster vaccination. A listing of SAEs at participant-level will be presented.
- A listing of concomitant medications at participant-level will be provided.

8. Summary of Changes to the Protocol

An interim analysis on immunogenicity assessment (anti-JE neutralizing antibody titer) collected at Visit 01 (Year 3 post primary vaccination) will be conducted in order to gain knowledge on whether or not a booster JE vaccine needs to be given sooner.

Reverse cumulative distribution curves for anti-JE neutralizing antibody titer will be produced at Year 3 and Year 4 post primary vaccination and 7 and 28 post booster vaccination to provide a visual presentation of the comparison of the antibody titers between study groups and how antibody titers change over time.

9. Reference

1. Wilson, E. B. (1927), Probable Inference, the Law of Succession, and Statistical Inference, *Journal of the American Statistical Association*, 22, 209–212.
2. Newcombe, R. G. (1998), Two-sided Confidence Intervals for the Single Proportion: Comparison of Seven Methods, *Statistics in Medicine*, 17, 857–872.
3. Newcombe, R. G. (1998), Interval Estimation for the Difference between Independent Proportions: Comparison of Eleven Methods, *Statistics in Medicine*, 17, 873–890.

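### SAP 6.3 plans no summary of the protocol's only exploratory endpoint (the IgM-seropositive proportion), and two of its four paired t-tests have a direction fixed by how the groups are defined

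*SAP*

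**What the plan says.** **Protocol.** Section 2.4 gives one exploratory immunologic endpoint: the proportion of participants seropositive for anti-JE IgM by ELISA, before the booster and 7 days after it. Section 4.5.2.2 plans the assay at both times, Section 5.1 repeats the variable, and Section 6.1 asks for the percentage with a Wilson score 95% CI without continuity correction, in order to tell a primary from a secondary response.

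**SAP.** Section 2.1.3 keeps that objective. Section 6.3.1 then states "The immunologic endpoints for exploratory analyses are as follows" and gives two items: "GMT of anti-JE neutralizing antibody at Year 4 prior to a booster dose of CD-JEV, 7 days, and 28 days after the booster dose", and the GMT ratios of Day 7 and Day 28 to Year 4. IgM enters only in 6.3.2, as a class criterion:

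- Primed, IgM criterion: "Primed group includes participants who will be seronegative for anti-JE immunoglobulin M (IgM) prior to the booster dose (Year 4) and 7 days after" (counted from vaccination).
- Primed, titre criterion: "who will have a 4-fold or higher response in anti-JE neutralizing antibody titer at 7 days post the booster dose in relation to pre-booster" (that is, against Year 4).
- Unprimed: IgM negative at Year 4, no four-fold rise at Day 7, and a change from below 1:10 to at least 1:10 "between Year 4 prior to the booster dose to 28 days after the booster dose".

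Within each class, Day 7 and Day 28 are compared with Year 4 "using a paired t-test to evaluate the magnitude of increase in GMTs for primed group and unprimed group", and the GMT ratios are given with 95% CIs. That makes 2 classes × 2 contrasts = 4 tests.

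SAP Section 8, which lists changes to the protocol, has two entries: the Year 3 interim analysis, and the plots ("Reverse cumulative distribution curves for anti-JE neutralizing antibody titer will be produced at Year 3 and Year 4 post primary vaccination"). The nearest output that could show IgM is in SAP 6.2: "Listing of serology results corresponding to each blood collection at participant-level will be provided".

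**The concern.** The exploratory objective is to separate a primary from a secondary antibody response at Day 7, and the IgM proportion is the measure the protocol chose for it. Followed as written, the SAP runs the assay and reports no IgM proportion and no interval.

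In its place the SAP reports tests within classes that are defined by the same titres being tested. Two of those tests ask whether titres rose in children who were admitted because their titres rose. A reader of the report could take the p-values as evidence that the booster worked in each class, when they only restate the entry rule.

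**Working it through.** **1. IgM endpoint, side by side**

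| Item | Protocol 2.4 and 6.1 | SAP 6.3 and 8 |
|---|---|---|
| Exploratory endpoint | IgM-seropositive proportion, Year 4 and Day 7 | PRNT-50 GMT and GMT ratio |
| Interval for IgM | Wilson 95% CI | none |
| Role of IgM | endpoint | class criterion |
| Change recorded | – | no |

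*Can the class sizes supply it?* Every Primed child is IgM negative at Day 7. Unprimed does not use Day-7 IgM, and children in neither class may be positive or negative. Class sizes therefore bound Day-7 positivity only between 0 and 1 minus the Primed share. For assumed Primed shares of 20%, 50% and 80%, that is 0–80%, 0–50% and 0–20%.

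*Would the restored endpoint be estimable?* The full Wilson width is 2z√[p(1−p)/n + z²/(4n²)] / (1 + z²/n). As a check, with n rounded down this formula reproduces all 40 cells of SAP Table 2. For example, Group A at 50% and 40% attrition has n = 655 × 0.6 = 393, and the width is 0.0993/1.0098 = 0.098. For assumed IgM positivity of 5–50% and attrition of 10–40%, with all enrolled children taken as tested, the width is 0.032–0.088 pooled, 0.036–0.098 in Group A and 0.073–0.194 in Group B.

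**2. The four paired contrasts, from the definitions alone**

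| Contrast | What the definition imposes | Direction fixed? |
|---|---|---|
| Primed, Day 7 vs Year 4 | every ratio ≥4 (log10 difference ≥0.602) | yes |
| Unprimed, Day 28 vs Year 4 | every child from <1:10 to ≥1:10 | yes |
| Primed, Day 28 vs Year 4 | Day 28 not used | no |
| Unprimed, Day 7 vs Year 4 | ratio <4 only | no |

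The last row has a caveat. If all titres below 1:10 are given one value, that contrast cannot be negative either. Two is therefore the count from the definitions alone.

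**3. Does a fixed direction guarantee p<0.05?** Not in a small group. The least favourable sample has one child at an assumed ceiling and the rest at the floor.

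- Primed Day 7, log2 ratios 2 to 10 (1,024-fold ceiling): at n=7 the mean is (6×2+10)/7 = 3.14, the SE is 8/7 = 1.14, t = 2.75, p = 0.033. The result is guaranteed from n=7.
- Unprimed Day 28, log2 ratios 1 to 10 (<1:10 set to 5): at n=12 the mean is (11+10)/12 = 1.75, the SE is 9/12 = 0.75, t = 2.33, p = 0.040. The result is guaranteed from n=12.
- With a 16,384-fold ceiling these become n=9 and n=15.

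**4. Simulation with no booster effect, only assay noise**

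- From the documents: N = 818×0.6 = 491 to 818×0.9 = 736 (SAP 2.3 attrition, all taken as boosted and tested), and 40–80% seroprotected at Year 4 (SAP Table 2).
- Borrowed: log2 titre SD 2.25, from the JEV05 new-facility GMT CI of 49.5–63.8, n=581 (Protocol Table 2): log2(63.8/49.5)/2 = 0.183; 0.183/1.964 × √581 = 2.25. This describes infants 28 days after the first dose, and it already contains some assay error. Its use at Year 4 is an assumption.
- Assumed: assay SD 0.3–1.0 log2, <1:10 set to 5, all children IgM negative. 500 runs per setting.

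| Assay SD (log2) | Primed group | Primed Day-7 test |
|---|---|---|
| 0.75–1.0 | median 10–57 children, ratio 5.4–6.3 | p<0.05 in every run with ≥3 children |
| 0.5 (N=491, 60%) | about 2 children | p<0.05 in all 235 runs with ≥3 children |
| 0.4 | median 0–1; 17–64 of 500 runs with ≥3 | p<0.05 in each of those |
| 0.3 | at most 2 of 500 runs with ≥3 | usually no test to report |

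The Unprimed Day-28 test gave p<0.05 in every run at each assay SD tried; at 0.75–1.0 the group held 20–58 children with a ratio of 3.0–3.7. At the same assay SDs, the Day-7 test in all boosted children gave a ratio of 1.00 and p<0.05 in about 3–7% of runs, as a valid test should. The two contrasts not fixed by definition also rejected in most runs at those SDs, because both classes favour children with a low Year 4 reading.

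**The case against.** **Low stakes.** Protocol Section 1 defines no hypotheses and calls the results descriptive, and SAP 3.6 says much the same. SAP 6.2 already plans paired comparisons of Day 7 and Day 28 with Year 4 in boosted children by study group, without selection on response. This stands: whether titres rise after the booster is addressed properly there. It limits the consequence, but does not make the two class-wise tests informative.

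**The endpoint is not lost.** The protocol still commits to it, the assay is planned, and the participant-level listing may show the values. That is fair, but a listing gives no proportion or interval, and the two documents then disagree on what will be reported.

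**Stronger readings a reader might infer, and why they fail:**

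- *That the IgM endpoint was deliberately removed.* Section 8 is not exhaustive: it also omits the seroconversion rate added in SAP 6.1. Its silence shows incomplete recording, not intent.
- *That small p-values are certain even if the booster did nothing.* For Primed this depends on the assay SD, which the documents do not give. With a precise assay few or no children would be Primed by noise, and the size of the class would itself be informative.
- *That all four tests are circular.* The definitions fix two.
- *That classifying on an early rise is the fault.* Protocol 4.4.1 argues for using the early response to recognise an anamnestic reaction. The fault is testing the rise afterwards in the same children.

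**Conclusion.** Both parts hold and both are confined to the exploratory analysis; primary and secondary conclusions are unaffected.

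The IgM gap is a matter of text and needs no assumption: two prespecified proportions (Year 4 and Day 7), none planned in the SAP, and no recorded reason. The fixed direction of the Primed Day-7 and Unprimed Day-28 tests follows from the definitions and also needs no assumption. Neither test is evidence of a booster effect. How often they would give p<0.05 without any effect does rest on the assumed assay SD, the borrowed titre SD and the value given to titres below 1:10, so the firm statement is that the direction is fixed, not that significance is guaranteed.

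This should be corrected, but it is not critical to the trial.

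**What to change.** 1. **IgM.** Add to SAP 6.3.1 the proportion seropositive for anti-JE IgM at Year 4 before the booster and at Day 7. Add to 6.3.2 the number and proportion at each time with a Wilson 95% CI without continuity correction. If removal was intended, enter it with the reason in Section 8 instead.
2. **The two fixed tests.** In 6.3.2 drop Day 7 vs Year 4 in Primed and Day 28 vs Year 4 in Unprimed. Also drop the 95% CIs of these two GMT ratios as inference against 1, or keep them as description only: a paired-t interval excludes 1 exactly when p<0.05, so removing only the p-value would leave the same circular inference. Keep the GMTs and ratios, with a note that the class definition constrains them.
3. **The other two comparisons.** Label Primed Day 28 and Unprimed Day 7 as conditioned on the selection, and refer to the unselected comparison in SAP 6.2 for the booster effect.

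Optional, and not part of the error: tabulate how many boosted children are Primed, Unprimed or neither, and state in SAP 3.4 the value used for titres below 1:10. The four-fold rule needs that value: a seronegative child with a Day-7 titre of 10 to below 20 has a four-fold rise if it is 2.5, but not if it is 5.

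Cost: SAP wording, one extra table from samples and assays already planned, and the loss of two uninformative exploratory p-values.

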6.3.2. Exploratory Immunogenicity Analysis

The antibody response to a booster dose of CD-JEV will be examined on the following two subgroups:

- Primed group includes participants who will be seronegative for anti-JE immunoglobulin M (IgM) prior to the booster dose (Year 4) and 7 days after the booster dose and who will have a 4-fold or higher response in anti-JE neutralizing antibody titer at 7 days post the booster dose in relation to pre-booster anti-JE neutralizing antibody titer at Year 4.
- Unprimed group consists of participants who will be seronegative for anti-JE IgM at Year 4 prior to the booster dose, who will not have a 4-fold or higher response in anti-JE neutralizing antibody titer at 7 days post the booster dose in relation to pre-booster anti-JE neutralizing antibody titer at Year 4, and who will seroconvert from negative (anti-JE neutralizing antibody titer $< 1:10$) to positive (anti-JE neutralizing antibody titer $\geq 1:10$) between Year 4 prior to the booster dose to 28 days after the booster dose.

GMTs of anti-JE neutralizing antibody along with their 95% CI will be provided for primed group and unprimed group at Year 4 prior to the booster dose, 7 days, and 28 days after the booster dose.

The GMTs at 7 days and 28 days post booster dose will be further compared to the GMTs at Year 4 prior to the booster dose using a paired t-test to evaluate the magnitude of increase in GMTs for primed group and unprimed group. The GMT ratio between 7 days post the booster dose and Year 4 and between 28 days post the booster dose and Year 4 will be provided along with its 95% CI.

7. Safety Analyses

7.1. Safety endpoints

The safety endpoints include:

- Frequency count and proportion of participants reporting immediate reaction occurring within 30 minutes of booster vaccination.
- Frequency count and proportion of participants reporting solicited local and systemic reactions occurring within 7 days of booster vaccination.
- Frequency count and proportion of participants reporting AEs and SAEs occurring within 28 days of booster vaccination.

7.2. Analysis of Safety endpoints

- The number and proportion of participants with at least one occurrence of an immediate reaction (local or systemic reaction, unsolicited AE, and SAE) occurring within 30 minutes of the booster vaccination will be tabulated by study group. The severity, relationship to the booster vaccination, status at 30 minutes (ongoing or not), medication given, and total number of the immediate reactions will be summarized by study group as well. Proportion of participants

will be based on the number of participants who are in safety analysis set. In addition, the immediate reaction will be listed at the participant-level.

- The number and proportion of participants with at least one occurrence of local reactions (ecchymosis, erythema, edema, induration, and pain/tenderness) and with at least one occurrence of systemic reactions (fever, change in eating habits, diarrhea, sleepiness, irritability, unusual crying, and vomiting) occurring greater than 30 minutes after receipt of the booster dose through 7 days post vaccination will be summarized by study group along with 95% CI of the percent. Each specific local or systemic reaction will be summarized by severity for each study group. A listing including the local and systemic reactions at the participant-level will be provided as well.
- The number and proportion of participants with at least one unsolicited AE occurring within 28 days of the booster dose along with 95% CI of the proportion will be presented by study group. The AEs will be summarized by maximum severity and relationship to the booster vaccination for each study group. The total number, maximum severity, relationship to the booster vaccination, onset date, status/outcome, duration for resolved cases (resolution date – onset date + 1), and medication given of AEs will be also summarized by study group. Summaries will be repeated for AEs found to be related the booster vaccination. A listing of AEs at participant-level will be presented.
- The number and proportion of participants with at least one SAE occurring within 28 days of the booster dose along with 95% CI of the proportion will be presented by study group. The SAEs will be summarized by maximum severity and relationship to the booster vaccination for each study group. The total number, maximum severity, relationship to the booster vaccination, onset date, status/outcome, duration for resolved cases (resolution date – onset date + 1), and medication given of SAEs will be also summarized by study group. Summaries will be repeated for SAEs found to be related the booster vaccination. A listing of SAEs at participant-level will be presented.
- A listing of concomitant medications at participant-level will be provided.

8. Summary of Changes to the Protocol

An interim analysis on immunogenicity assessment (anti-JE neutralizing antibody titer) collected at Visit 01 (Year 3 post primary vaccination) will be conducted in order to gain knowledge on whether or not a booster JE vaccine needs to be given sooner.

Reverse cumulative distribution curves for anti-JE neutralizing antibody titer will be produced at Year 3 and Year 4 post primary vaccination and 7 and 28 post booster vaccination to provide a visual presentation of the comparison of the antibody titers between study groups and how antibody titers change over time.

9. Reference

1. Wilson, E. B. (1927), Probable Inference, the Law of Succession, and Statistical Inference, *Journal of the American Statistical Association*, 22, 209–212.
2. Newcombe, R. G. (1998), Two-sided Confidence Intervals for the Single Proportion: Comparison of Seven Methods, *Statistics in Medicine*, 17, 857–872.
3. Newcombe, R. G. (1998), Interval Estimation for the Difference between Independent Proportions: Comparison of Eleven Methods, *Statistics in Medicine*, 17, 873–890.

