#### **3.3. Previous experience with CD-JEV**

CD-JEV has been used since 1988, with over 400 million doses administered internationally. The vaccine is currently licensed in twelve countries, and, in 2013, vaccine produced at a newly constructed Good Manufacturing Practice (GMP) compliant production facility was prequalified by the World Health Organization (WHO). Following prequalification, CD-JEV was also selected for use in the 2015 GAVI-supported catch-up campaigns in children less than 15-years-old.

Like other parenterally administered vaccines, vaccination with CD-JEV vaccine may cause local and systematic side effects in some children. These include pain at the injection site for a short while after injection and swelling, redness, and tenderness at the injection site. Fever may occur and, in some cases, a rash may appear in the initial days following the vaccination. Because CD-JEV is a live attenuated vaccine, there is a theoretical risk that systemic disease including encephalitis could occur if the vaccine strain replicates unchecked. To date, this has not been reported with CD-JEV. No reports of severe allergic reactions or death have been associated with CD-JEV.

From 2005-2008, the WHO Global Advisory Committee on Vaccine Safety (GACVS) and the WHO Strategic Advisory Group of Experts (SAGE) on Immunization reviewed the safety of CD-JEV and other JE vaccines. These reviews stated that CD-JEV is well tolerated across a wide age range and can safely be given to children as young as 9 months of age. The reviewers noted that no SAEs were attributed to CD-JEV in 12 clinical studies conducted from 1992 through 2008 in China, India, the Philippines, South Korea, Sri Lanka, and Thailand. In 2013, the WHO GACVS reviewed the safety of CD-JEV again and concluded that it had an excellent safety profile.

Seroprotection rates following a single dose of CD-JEV ( $\geq 10^{5.4}$  plaque-forming units) have been greater than 90% in most clinical trials. Several early Chinese studies have shown a dose-response gradient with 85% to 100% seroconversion after a single dose of CD-JEV vaccine was given to children 1 to 12 years of age. In one of the first immunogenicity studies performed outside of China, 95% of participants aged 9 to 15 months were

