### 3.5. Potential risks and benefits

#### 3.5.1. Potential risks

The child may experience discomfort and pain from venipuncture for collection of 2 ml of blood. Venipuncture is sometimes associated with discomfort during phlebotomy, and rarely, an infection at the site of phlebotomy if improperly conducted. The child may experience discomfort, pain, redness, swelling, and/or local hardness at the injection site.

Like any vaccine, vaccination with CD-JEV may cause side effects in some children. The side effects of JE vaccination may include pain at the injection site for a short while after injection and swelling, redness, and tenderness at the injection site. Fever may occur and in some cases a rash may appear in the initial days following the vaccination. Because the vaccine is a live attenuated vaccine, there is a very small theoretical risk that encephalitis, or infection of the brain, could occur. However this has never been reported to occur with CD-JEV. Allergic reactions and death, while rare, are also possible with any vaccination.

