## 4. RESEARCH DESIGN AND METHODS

The proposed study is a phase 4 open-label trial enrolling up to 818 Bangladeshi children who had previously participated in JEV05, a PATH-supported clinical study conducted from May to December 2012 during which 10- to 12-month-old infants were given a single dose of CD-JEV. Eligible JEV05 participants who still live in the

area will be identified using the local health and demographic surveillance system (HDSS) and asked to participate. Children will be divided into two groups based on whether they received vaccine from the old or new facility in JEV05:

- Group A (up to 655 eligible): children randomized to Groups 2-4 (new facility) in JEV05.
- Group B (up to 163 eligible): children randomized to Group 1 (old facility) in JEV05.

An overview of the study activities is provided in Table 3. A 2 ml blood sample will be collected from all participants three and four years after initial vaccination. The sera will be tested using PRNT; JE neutralizing antibody titers  $\geq 1:10$  will be considered seroprotective.

After the blood draw at Visit 02 occurring in May to December 2016, four years after their initial vaccination, both groups will receive a single subcutaneous booster dose of CD-JEV. Additional serum samples will be collected on Day 7 and Day 28 following the booster dose for measurement of serum anti-JE neutralizing antibody titers.

Following the booster dose, children will be monitored for immediate reactions during the first 30 minutes, solicited injection site and systemic adverse reactions for 7 days, unsolicited adverse events and serious adverse events for 28 days. All safety events will be identified or observed by study staff during home visits, clinic visits, and/or reported by a parent or legal guardian. Solicited and systemic adverse reactions will be assessed through home visits 1 through 6 days following vaccination, and a fixed site clinic (FSC) visit on Day 7 following vaccination. Information regarding unsolicited AEs occurring in the 28 days following vaccination will be collected and recorded on a standard questionnaire during clinic visits. Events will be graded for severity and assessed for relatedness to vaccination by the investigator.

The study will be open-label; no placebo control will be employed and safety assessments will be unblinded.

[figure not shown]

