#### 4.4.4. Home follow-up visits (Visit 03 through Visit 08, 1-6 days post vaccination $\pm$ 0 day)

A field worker will visit the participant at home to:

- Inquire about the child's health (any illnesses or medications taken or visits to a healthcare facility).
- Inquire about any reactions using a standard questionnaire to record the local and systemic reactogenicity after vaccination.

- Remind the parents that they will need to bring their child to the FSC on the 7th day (+ 3 days) following vaccination for a blood draw and to check on the welfare of the child.
- Remind the parents to seek medical care as appropriate and inform the investigator as soon as possible in the event of an adverse reaction or SAE. If the child visits a health care provider, the parents should be sure to inform him/her of the child's participation in the study and present the provider with contact information for the investigator as indicated on the study identification card.
- Complete the appropriate section(s) of the CRF.

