#### **7.2.3.2. Local and systemic signs and symptoms**

All participants will be monitored for assessment of local and systemic signs and symptoms occurring from 30 minutes through 7 days post vaccination. Study staff will inquire about specific (solicited) local and systemic signs and symptoms and other unsolicited adverse events.

Using a standardized data collection instrument the following local and systemic signs and symptoms will be documented and graded on predefined scales based on functional assessment or magnitude of reaction. Any local and systemic reaction that meets the criteria for a serious adverse event must also be documented on an SAE form.

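### Rash is named twice as an effect of this vaccine but is not solicited, so it has no daily prompt by name and no planned rate

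*SAP*

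**What the plan says.** Protocol 3.3 describes experience with CD-JEV: "Fever may occur and, in some cases, a rash may appear in the initial days following the vaccination". Protocol 3.5.1 repeats this among the risks: "Fever may occur and in some cases a rash may appear in the initial days following the vaccination". The other systemic harms are put differently. Encephalitis is called a theoretical risk, and for the rest the text says "Allergic reactions and death, while rare, are also possible with any vaccination".

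The solicited lists are the same in both documents. SAP 7.2 gives the systemic terms as "systemic reactions (fever, change in eating habits, diarrhea, sleepiness, irritability, unusual crying, and vomiting" and the local terms as "local reactions (ecchymosis, erythema, edema, induration, and pain/tenderness"; Protocol 7.2.3.2 has the same seven and five. A rash would therefore be recorded as an unsolicited adverse event.

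On how such events are found, Protocol section 4 says "Information regarding unsolicited AEs occurring in the 28 days following vaccination will be collected and recorded on a standard questionnaire during clinic visits", and SAP 2.2 says the same. Protocol 7.2.3.2 says of the first seven days: "Study staff will inquire about specific (solicited) local and systemic signs and symptoms and other unsolicited adverse events". At each home visit on Days 1 to 6, the field worker's tasks under Protocol 4.4.4 begin "Inquire about the child's health (any illnesses or medications taken or visits to a healthcare facility". Table 3 of the protocol marks the recording of reported adverse events at those visits too.

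**The concern.** The safety profile of the booster is a secondary objective, and the study is meant to inform policy on a second dose. A reader would expect each effect that the protocol itself attributes to the vaccine to be asked about by name and reported with a rate. Rash is the exception. At stake is whether the study report can state how often rash followed the booster in the first week, on the same footing as fever or injection-site redness. The plan does not provide for that figure, and the information behind it may be gathered less completely than for the named symptoms.

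**Working it through.** The documents contain no rash rate, capture rate or safety precision figure, so there is nothing to reproduce. The check compares sections.

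**1. Named effects against solicited terms.**

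| Effect named in Protocol 3.3 or 3.5.1 | Solicited term |
|---|---|
| Injection-site pain | Pain/tenderness |
| Tenderness | Pain/tenderness |
| Swelling | Edema |
| Redness | Erythema |
| Local hardness (3.5.1 only) | Induration |
| Fever | Fever |
| Rash | None |

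Solicited terms: 7 systemic + 5 local = 12, and rash is in 0 of 12. Section 3.3 names six effects, of which five are covered; with local hardness from 3.5.1 there are seven, of which six are covered. Rash is the only omission on either count. Two systemic effects are described as occurring, fever and rash, and one of the two is solicited. Conversely, six of the seven solicited systemic terms (all but fever) are not named as CD-JEV effects in those two sections.

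**2. What will be reported.** For solicited reactions, SAP 7.2 summarises each specific reaction by severity and study group, and Protocol 6.2 calls for exact 95% confidence intervals. For unsolicited events, SAP 7.2 gives the proportion with any event and its interval. It then summarises by maximum severity, relationship, onset date, outcome, duration and medication, and adds a participant-level listing. Protocol 6.2 likewise specifies a listing and summaries by severity and relationship. Neither specifies a table by event term. A rash would be identifiable only in the listing. Because onset dates are recorded, a count through Day 7 could be extracted afterwards, but none is planned. This gap does not depend on how well rash is captured.

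**3. How a rash would be found.** Protocol section 4 and SAP 2.2 place the recording of unsolicited events at clinic visits, which after the vaccination day fall at Days 7 to 10 and 21 to 35 (Protocol Table 4). Against that:

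- Protocol 7.2.3.2 has staff ask about other events through Day 7 and grades unsolicited reactions in that window on the functional scale used for the non-fever systemic symptoms.
- Protocol 4.4.4 has a daily question on the child's health and a standard questionnaire on reactions.
- Table 3 records events at Visits 03 to 08.

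The Visit 09 examination adds little. Table 3 marks it, but the Visit 09 procedures in 4.4.5 do not list it, its content is not defined (the Visit 01 and 02 examinations name the skin), and a rash may have faded by then.

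**4. Size of any shortfall.** Let c be the share of rashes captured without a named prompt. The reported rate is the true rate × c, and the proportional shortfall is 1 − c. Both c and the true rate are unknown. For assumed values of c:

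- c = 1.00: shortfall 0%
- c = 0.75: shortfall 25%
- c = 0.50: shortfall 50%

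Case counts would add nothing firm. The 10% to 40% attrition in SAP 2.3 gives 818 × 0.90 = 736 to 818 × 0.60 = 491 children enrolled at Year 3. The number boosted is not given and may be lower, after the Visit 02 exclusions and further losses.

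**The case against.** The strongest reply is that staff are in the home on each of Days 1 to 6 and ask about health and reactions, that the protocol requires inquiry about other events through Day 7, and that such events are graded. The choice of solicited terms is a matter of design, and the protocol says only that rash may appear in some cases. SAP 7.2 also reproduces the protocol's list faithfully, so the SAP introduced no error.

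Much of this stands. A reader might infer that rash will be under-counted, or that a rash beginning on Day 2 and gone by Day 5 would be known only if a parent volunteered it. The documents do not support either inference: Protocol 4.4.4, 7.2.3.2 and Table 3 all provide for asking or recording during those days, and full capture remains possible. A reader might also suppose that rash will at least appear in a 28-day table of unsolicited events; SAP 7.2 specifies no such table by term.

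Two things survive. An open question is not a named prompt, and one about illness, medication and care may not bring out a mild, brief rash. And the lack of any planned rash tabulation is untouched by the argument about capture. That the list originates in the protocol means only that the remedy must start there.

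**Conclusion.** The point holds in two parts of different strength.

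- **Certain as written:** rash is named twice as an effect of CD-JEV, is in none of the 12 solicited terms, and has no planned rate, confidence interval or seven-day count.
- **Plausible but unquantified:** rash may be under-ascertained relative to the solicited symptoms. The range of 0% to 50% rests wholly on an assumed capture of 100% to 50%, and no number of missed cases can be given.

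Section 4 of the protocol and SAP 2.2 also sit awkwardly with Protocol 7.2.3.2 and Table 3 on when unsolicited events are collected. The primary immunogenicity objective is unaffected. The point deserves action because it bears on what the safety objective can report and the remedy is small.

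**What to change.** Add rash to the systemic reactions in Protocol 7.2.3.2 and to the structured reactogenicity form used at Visits 03 to 09, graded on the functional scale already there. Add it to the systemic list in SAP 7.2, so that it is tabulated by severity through Day 7 with a 95% confidence interval.

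If the form can no longer change, add to SAP 7.2 a table of unsolicited events by event term and study group, restricted to onset through Day 7, with 95% confidence intervals. This needs no new data and closes the reporting gap, but not any gap in ascertainment. A footnote should give the number of imputed onset days: SAP 3.3.1 sets a missing day to the vaccination day when month and year agree, which would place the event inside the window.

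In either case, reconcile Protocol section 4 and SAP 2.2 with Protocol 7.2.3.2 and Table 3, so that it is clear whether unsolicited events are asked about and recorded at home visits as well as clinic visits.

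The cost is one line on a form already completed daily, a minor protocol amendment and a small SAP change. The drawback is that a prompted rash rate is likely to be higher and less comparable with studies that did not solicit rash; the report should say so.
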